9.5 Safety Analyses

Safety will be assessed through the incidence of AEs and SAEs, which will be coded using MedDRA. The number and percentages of patients reporting AEs and SAEs will be summarized at the MedDRA system organ class and preferred term level. As a secondary endpoint of the study summaries will be provided for AEs and SAEs related to the study device, as well as for AEs and SAEs related to the study procedure. Related events are those where the relationship is indicated as Possible, Probable, or Causal relationship. Summaries of all AEs and SAEs reported within the first 30 days after the initial ablation procedure will be generated. All reported adverse events will be listed. Listings will also be provided for concomitant procedures and concomitant medications.

Safety endpoints are as follows:

- All AEs
- Serious AEs
- All AEs related to the study device
- Serious AEs related to the study device
- All AEs related to the study procedure
- Serious AEs related to the study procedure

9.6 Additional Endpoints Analyses

Counts and percentages will be provided for patient performance status as measured by the Eastern Cooperative Oncology Group (ECOG) classification at each visit. Changes in ECOG will be summarized using shift tables. A listing will be provided for ECOG performance status.

Summary statistics will be provided for the hematology parameters and chemistry parameters at each visit. Summary statistics of changes in hematology and chemistry parameters from visit 1 to visit 2, visit 1 to visit 3, and visit 2 to visit 3 will be presented.

Liver tissue assessment including severity of steatosis and cirrhosis, presence of lesion microsatellite instability, phenotype, presence of microvascular invasion, BCLC staging system, and Child-Pugh score will be summarized with number and percentages in each category.

Target lesion assessments including lesion type, shape, segments, depth, maximum dimension by X-, Y-, and Z-axis will be summarized with statistics appropriate for categorical or continuous variables. A listing for target lesion will be produced that will include subject ID, visit, lesion number, type of lesion, shape of lesion, segment number, imaging modality used for lesion measurements, liver lesion dimension, and evidence of target lesion recurrence. The listing will be presented by sorting the patient followed by visit, lesion number and segment.

Ablation procedure details that include type of anesthesia, imaging modalities used for guidance/probe placement and margin assessment, number of CT images performed for probe placement and margin assessment, liver stiffness near ablation site, amount of contrast used, duration of procedure, and total radiation exposure from the CT scanner will be summarized with statistics appropriate for categorical or continuous variables.

Ablation including lesion type, lesion number, probe used, segments, duration, max power observed, max temperature observed, and repositioning will be summarized with statistics appropriate for categorical or continuous variables.

Listing for ablation procedure will include subject ID, Number of CT scan(s) performed for probe placement, Duration of the ablation procedure, Total duration of ablation, Were there any repositions in probes during ablation and how many, reason of probe reposition, Number of CT scan(s) performed for margin assessment, Duration of the AC imaging, and Overall procedure duration.

Listing for ablation will include subject ID, lesion type, lesion number, probe, probe type, segment, Max power observed, Max temperature observed, dynamically change power during this ablation cycle for a specific probe, type of power change, and assessment of margins using CT & ablation confirmation software after ablation. The listing will be presented by sorting the patient and by lesion number.

Listing for ablation outcome will include subject ID, lesion type, lesion number, outcome of the ablation, reason for incomplete ablation, and smallest margin distance in the ablation zone.

Listing for ablation confirmation will include subject ID, lesion type, lesion number, use of ablation confirmation software to validate probe placement, actions in probe placement, type of actions taken in probe placement, reason for taking no actions, use of NeuWave ablation confirmation software to validate margin assessment, % of contraction used, actions taken regarding margin, type of actions taken regarding margin, and reasons for No actions taken despite AC software indicating ablation margin was not complete.

9.7 Plans for Interim Analysis

There are no planned interim analyses.

9.8 Handling of Missing Data

All analyses will be performed only on patients who had the ablation procedure with the AC software tool attempted and only observed data will be analyzed. There will be no imputation of missing data for any parameters or for early terminated patients.

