The Sponsor may terminate a site or the study at any time. When this occurs all patients at the site will be withdrawn and documented as early termination. Reasons for site or study termination may include, but are not limited, to the following:

- Administrative concerns (e.g., inadequate patient enrollment, Investigator/institution non-compliance, change of business strategy, etc.).
- Safety issues, including reaching any of the complication thresholds, including those due to non-compliance, which substantially affect the risk-to-benefit ratio of the study patients at a site or for the study as a whole.
- Regulatory body mandates.

The Investigator also has the right to terminate subject or site participation at any time (e.g., for safety reasons or inability to enroll patients). Should termination of a site be necessary, the Sponsor will provide procedures for termination.

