8.3 Visit 3: 6 Weeks Follow-up

Six weeks (\pm 3 weeks) after the ablation procedure, the patient will visit the study site and the following assessments will occur:

- Evaluate ECOG performance status.
- Perform laboratory tests, as follows:
 - Coagulation tests, including APTT or PTT, PT, and PTA are to be performed, as applicable, per site SOC, but INR is required.
 - As applicable, per site SOC, liver function tests, including ALB, ALK, ALT, AST, T/D bilirubin, GGT, and TP.
 - As applicable, per site SOC, renal function tests, including BUN, creatinine, and electrolytes (sodium, potassium, chloride, and bicarbonate).
 - Alpha-fetoprotein, as per site SOC.
 - Carcinoembryonic antigen, as per site SOC.
- Record any new relevant concomitant medications or changes to existing relevant concomitant medications (i.e., chemotherapy, blood-thinning/coagulation, NSAIDs, steroids, medications used to treat AEs, and medications used to treat hepatitis, if concurrently treating).
- QOL questionnaires: EORTC QLQ-C30 and the liver-specific QLQ-HCC18.
- Pain score, using the Numeric Pain Rating Scale.
- Determine soft-tissue lesion(s) details (e.g., size, lesion type, location, shape) via CT or MRI.
 - If CT is used with contrast, record the amount of contrast used.
 - Review soft-tissue lesion(s) details to determine if there is recurrence or progression of the ablated lesion(s). Note: No additional ablation procedures should be performed at this visit as part of this study. If the patient has a progression, they should be treated outside of this study

protocol.

- Record any new, liver-related concomitant procedures.
- Evaluate Technique Efficacy, defined as ablation of the target lesion(s) according to the protocol and covered completely, with an adequate margin, as defined by the performing physician (that is, the ablation zone completely overlaps or encompasses the target lesion plus an ablative margin), as assessed by imaging, at Visit 3.
- Record any potential device-related or procedure-related AEs or any SAEs.
- Record date of study completion (Visit 3, or upon patient's early withdrawal).

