- Post-ablation syndrome (body's response to the destroyed lesion appearing as flu-like symptoms, including fever, decreased appetite, and general discomfort occurring most typically 3 to 5 days after the ablation procedure)
- Skin burn
- Thrombosis (local coagulation or clotting of the blood in the circulatory system, with or without tube drainage)
- Tumor implantation

QOL questionnaires will be summarized with methodology consistent to the recommendations of the specific survey. Additional endpoints will be summarized with descriptive statistics.

Plans for Interim Analysis

There are no plans for interim analyses whose intent will be to stop the study early or to adapt the study design or planned number of patients.

Ongoing Review

The Sponsor will also review complications periodically, as per the Safety Management Plan.

Analysis of Safety

The analysis of safety is summarized above under Primary and Secondary Endpoint Analyses.

Handling of Dropouts or Missing Data

All analyses will be performed only on patients undergoing ablation with the AC software tool and only observed data will be analyzed. There will be no imputation of missing data for any parameters or for early terminated patients.

Multicenter Studies

No adjustment for center is planned in the statistical analysis. However, center specific analyses may be conducted pending within-center sample size to understand the effect of the performing physician's techniques and the study site's SOC may have on the overall results.

Analysis of Subgroups

No subgroup analyses are currently planned but may be considered pending the distribution of baseline demographic and clinical characteristics. Subgroup analyses, if performed, will be specified in the Statistical Analysis Plan.

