1.1 Study Objectives

The primary objective of the study was to examine whether the feedback from the AC software impacts the performing physician's (i.e., the individual performing the ablation procedure) decision making in terms of probe(s) position, ablation time, or number of ablations based on insufficient ablation margins based on the following assessments:

- a. Percentage of repositions informed by AC due to sub-optimal probe placement.
- b. Percentage of re-ablations informed by AC due to insufficient ablation margins.

The secondary objectives were the following:

1. Technical success - defined as ablation of the target lesion(s) according to the protocol and covered completely with an adequate margin, as defined by the performing physician (that is, the ablation zone completely overlaps or encompasses the target lesion plus an adequate ablative margin). Technical success will be assessed by the performing physician using AC as a tool immediately following the procedure.
2. Technique efficacy - defined as ablation of the target lesion(s) according to the protocol and covered completely, with an adequate margin, as defined by the performing physician (that is, the ablation zone completely overlaps or encompasses the target lesion plus an ablative margin), as assessed by imaging at Visit 3.
3. Hospital resource utilization based on:
 - a) Length of post-ablation hospital stay.
 - b) Time to perform procedure, which includes 3 measures of time:
 - Overall procedure duration, defined as the time elapsed between loading CT dataset into the AC system and completion of MWA with last probe removal.
 - AC imaging duration, defined as the time elapsed between loading CT dataset into AC to plan for the target ablation and last use of AC to plan for the final ablation.
 - Ablation duration, defined as the time elapsed between ablation first probe puncture and removal of the last probe at the completion of the ablation.
4. Device and procedure safety through the monitoring of adverse events. Patients will be evaluated for all device-related and procedure-related AEs and all SAEs from the time of the first probe puncture (Visit 2) through study completion (Visit 3).
5. Device User Experience questionnaire will be completed by the performing physician. The first half will be completed following each ablation procedure and the second half will be completed approximately every 5 ablations (per treating physician).

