9.4.2 Secondary Endpoints Analyses

1. Technical success: The number and percentage of lesions achieving technical success will be summarized and an exact 95% confidence interval will be provided. Analysis will be conducted using FAS and PP analysis sets. Technical success is captured on the “Ablation Outcome” form on eCRF. Technical success is achieved when the treating physician choose the response as “complete ablation” for the question “Per treating physician, what was the outcome of the ablation?”. The summary statistics will also be presented for per patient. The technical success is considered achieved at a patient-level when all treated lesions for a patient were successful.

2. Technique efficacy: The number and percentage of lesions achieving technique efficacy will be summarized and an exact 95% confidence interval will be provided. Analysis will be conducted using FAS and PP analysis sets. Technique efficacy is captured on the eCRF based on the response as “yes” from the physician performing ablation for the question “Was technique efficacy achieved for target lesion?” from the “Technique Efficacy” form. The summary statistics will also be presented for per patient. The technique efficacy is considered achieved at patient-level when all treated lesions for a patient were successful.

3. Hospital resources utilization: Summary of endpoints related to hospital resources utilization will include number of patients (N), mean, standard deviation, median, minimum, and maximum and will be based on FAS. Following endpoints will be presented on the summary tables:

a) Length of post-ablation hospital stay. Length of post-ablation hospital stay will be derived from the Discharge and Ablation forms on eCRF. It will be derived as

Length of post-ablation hospital stay = (date and time of hospital discharge – date and time of ablation ended).

b) Time to perform procedure, which includes 3 measures of time:

i) Overall procedure duration, defined as the time elapsed between loading CT dataset into the AC system and completion of MWA with last probe removal. The overall procedure duration is captured on the Ablation Procedure form on eCRF.

ii) AC imaging duration, defined as the time elapsed between loading CT dataset into AC to plan for the target ablation and last use of AC to plan for the final ablation. AC imaging duration is captured on the Ablation Procedure form on eCRF.

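### Technique efficacy is estimated from observed Visit 3 assessments only, with no stated denominator and no bounds for unassessed lesions, so the rate may be overstated

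*SAP*

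**What the plan says.** SAP 1.1 defines technique efficacy as complete coverage of the target lesion with a margin, "as assessed by imaging at Visit 3". SAP 9.4.2 takes the result from the physician's yes on the Technique Efficacy form and plans this summary: "The number and percentage of lesions achieving technique efficacy will be summarized and an exact 95% confidence interval will be provided". It is to be run on the FAS and the Per Protocol set. For patients, the rule is: "The technique efficacy is considered achieved at patient-level when all treated lesions for a patient were successful".

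SAP 9.8 governs missing data: "only observed data will be analyzed", and "There will be no imputation of missing data for any parameters or for early terminated patients". Protocol 10.9 has the same rule: "All analyses will be performed only on patients undergoing ablation with the AC software tool and only observed data will be analyzed".

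Three further provisions decide who can be in the FAS without a Visit 3 result:

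- SAP section 6 admits patients in whom ablation was attempted with the AC tool, identified by AC having been used to check probe placement.
- Protocol 6.7 allows withdrawal during the procedure, for example when the lesion cannot be located and targeted. A patient who could not be ablated and had no adverse event at puncture is discontinued. The same section covers death, withdrawal of consent and loss to follow-up.
- On termination of a site or the study, Protocol 6.7 says: "When this occurs all patients at the site will be withdrawn and documented as early termination". SAP section 7 confirms that this study stopped early.

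SAP 9.4.2 states no denominator for technique efficacy, although SAP 9.4.1 spells out the denominators of both primary endpoints. No sensitivity or bounding analysis is planned.

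**The concern.** A lesion without a Visit 3 assessment has no observed value, so under SAP 9.8 it drops out of both numerator and denominator. That is harmless only if unassessed lesions would have succeeded as often as assessed ones. At least one route out is linked to outcome: a procedure attempted with AC but not completed puts the patient in the FAS and then ends participation. Death and withdrawal may also be linked.

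The study's stated purpose is estimation, so a rate whose denominator is implicit and whose missing part is not bounded weakens the result itself. The planned exact interval measures sampling error among assessed lesions and is silent on the unassessed.

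There is also a gap at patient level. Up to three lesions may be ablated, and success requires all treated lesions to succeed. Nothing says how to classify a patient with one successful and one unassessed lesion, so two programmers could report different patient-level rates.

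**Working it through.** **The plan's own figures.** The documents give no expected rate, dropout rate or precision for technique efficacy. The only precision statement concerns the repositioning rate (SAP section 7): 15%, 100 patients, 95% half-width below 7%. It reproduces under the normal approximation: 1.96 × √(0.15 × 0.85 / 100) = 6.998%. It does not bear on technique efficacy.

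**Formula.** Let m be the share of FAS lesions not assessed at Visit 3, p_obs the success rate among assessed lesions, and p_mis the rate among unassessed lesions.

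- True rate over all FAS lesions = (1 − m) × p_obs + m × p_mis
- Bias of the observed-only rate = p_obs − true rate = m × (p_obs − p_mis)
- Largest upward bias (p_mis = 0) = m × p_obs
- Worst case = x/N and best case = (x + missing)/N, where x is the number of observed successes and N the number of FAS lesions. The two bounds lie m apart.

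**Worked example (all inputs assumed).** N = 60 lesions, 6 unassessed (m = 10%), 51 successes among the 54 assessed. Intervals are Clopper-Pearson.

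| Rule | Rate | 95% CI |
|---|---|---|
| Observed only | 51/54 = 94.4% | 84.6 to 98.8 |
| Worst case | 51/60 = 85.0% | 73.4 to 92.9 |
| Best case | 57/60 = 95.0% | 86.1 to 99.0 |

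The possible error is lopsided: 9.4 points in one direction and 0.6 in the other.

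**Dependence on p_mis**, same example, bias = 0.10 × (0.944 − p_mis):

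| p_mis | Bias (points) |
|---|---|
| 0% | +9.4 |
| 50% | +4.4 |
| 80% | +1.4 |
| 94.4% | 0 |
| 100% | −0.6 |

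**Dependence on the missing share**, assumed N = 100:

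| Missing | Observed only | Worst to best case |
|---|---|---|
| 5 | 86/95 = 90.5% | 86.0% to 91.0% |
| 10 | 81/90 = 90.0% | 81.0% to 91.0% |
| 20 | 72/80 = 90.0% | 72.0% to 92.0% |
| 5 | 90/95 = 94.7% | 90.0% to 95.0% |
| 10 | 86/90 = 95.6% | 86.0% to 96.0% |
| 20 | 76/80 = 95.0% | 76.0% to 96.0% |

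**The case against.** **The rule is prespecified and the stakes are modest.** Protocol and SAP agree on it. The endpoint is one of seven secondary items in a descriptive study with no hypotheses, and follow-up is short. All of this stands, and it limits the weight of the point.

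**A reader might infer that the rate is biased upward as a matter of fact.** The documents do not show that. The sign depends on p_mis, and nothing in them says that unassessed lesions do worse. Withdrawals caused by study termination are administrative: SAP section 7 gives slow enrolment and overlapping studies as the reasons for stopping. Such losses need not relate to lesion outcome, and nothing shows that any treated patient was still in follow-up at that time.

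**A reader might infer that patients treated elsewhere for progression drop out.** Protocol 8.3 does say "If the patient has a progression, they should be treated outside of this study", but it refers to progression found at Visit 3, when the imaging is done. Such a patient is assessed, not missing. Re-treatment before Visit 3 is simply not addressed.

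**The denominator might be all FAS lesions.** SAP 9.4.2 counts recorded successes and names the FAS, so unassessed lesions could be read as not achieved. SAP 9.8 makes the observed-only reading the more natural one. That both can be argued is a reason to state the denominator.

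**Bounds can be derived without a new table.** SAP 9.2 tabulates discontinuations with reasons, and SAP 9.1 lists all case report form data by patient. A reader with the listings could construct the bounds. The disposition table alone works by patient, however, and gives neither the number of lesions without a Visit 3 assessment nor the recalculated rates.

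**Counting death as failure changes the estimand.** Correct: the definition concerns coverage on imaging. Death therefore counts as not achieved only in the worst-case bound.

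**Conclusion.** The point holds as a risk and an omission. SAP 9.8 read with 9.4.2 confines technique efficacy to lesions with an observed Visit 3 assessment. FAS lesions can leave the percentage by several documented routes, one of them linked to the outcome of the procedure. The plan does not state the denominator, classify partly assessed patients, or bound the effect.

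The rate may be overstated by at most the missing share times the observed rate. At an observed 90%, that is 4.5, 9.0 and 18.0 points for 5%, 10% and 20% missing; at 95%, it is 4.75, 9.5 and 19.0 points. These maxima require every unassessed lesion to have failed. With equal success rates the bias is zero, and it is slightly negative if the unassessed do better. All these shares and rates are assumptions, so the actual size is unknown.

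The stated rule can be defended for a descriptive secondary endpoint. Adding bounds is a cheap improvement to it.

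**What to change.** Keep the observed-case analysis and make these additions for technique efficacy:

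1. State in SAP 9.4.2 that the observed-case denominator is the FAS (or Per Protocol) lesions with a Visit 3 assessment, and print that number beside the FAS total.
2. Add worst-case and best-case rates with exact 95% confidence intervals over all FAS lesions. Unassessed lesions count as not achieved in the worst case and as achieved in the best case.
3. Do the same over all FAS patients. A patient with any unassessed lesion is not achieved in the worst case and is classified by the assessed lesions in the best case. To match the lesion-level bound, a patient with no assessed lesion counts as achieved in the best case.
4. Tabulate lesions without a Visit 3 assessment by reason: death, withdrawal of consent, loss to follow-up, ablation attempted but not completed, study or site termination, and Visit 3 attended but lesion not assessed.

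The cost is one extra table and a few lines of text. The bounds need only FAS membership and the presence or absence of a Visit 3 result, both already collected. Patient-level reasons come from the completion and discontinuation form. No imputation model is needed. If outputs have already been produced, SAP 9.1 provides for identifying and documenting the addition in the clinical study report. The downside is that a less favourable figure appears beside the observed one.

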9.9 Multicenter studies

No adjustment for center is planned in the statistical analyses.

